3.3 Study Groups

This is a double blinded study. Neither the participants nor the study team will know which group the participant has been assigned to. Records of the assignment will be kept with the pharmacist and can be accessed by the study team immediately in case of adverse events.

All study participants will undergo the same study procedures for screening and on the follow up visits. Women with symptomatic uterine fibroids planning to undergo surgery will be screened for participation.

Those found to be eligible will undergo pre-study evaluation during the screening period including:

- 1) Complete clinical evaluation.
- 2) Inclusion and exclusion criteria.
- 3) Uterine fibroid symptom and quality-of-life (UFS—QoL) questionnaires.
- 4) Fibroid number, location and size using ultrasound, and MRI if ultrasound is inconclusive.
- 5) Endometrial biopsy (if not done in the last 12 months).
- 6) Cervical smear (if not done in the last 12 months).
- 7) Lab: complete blood count, ferritin, liver enzymes, lipid panel.

We will use stratified block randomization with randomly permuted blocks of sizes 4 and 6 into one of the two arms. The randomization scheme will be stratified by race/ethnicity in three categories: African American, Caucasian, and Hispanic. All other races will be excluded (small numbers precludes proper stratification and analysis). The stratification will ensure similar distribution of race/ethnicity categories across the arms.

This is an “add-on” study, i.e. subjects in both arms will continue their current treatments for fibroids except hormonal birth control and medications contraindicated as per simvastatin prescribing information.

After 12 weeks of treatment, study participants will be re-evaluated, both clinically and by imaging. The results of the ultrasound will be discussed with the study subjects and they will be counselled about the need for the surgery if there are significant changes in fibroid size.

The fibroid tissue samples will be obtained for examination after the surgery (either myomectomy or hysterectomy). The fibroid tissue samples will be obtained for examination after the surgery (either myomectomy or hysterectomy). The study team will collect a 2.5 X 2.0 X 1.0 cm (or up to half of the tumor size) tissue sample from one fibroid for this study after the surgical pathology team has completed a preliminary evaluation of the delivered uterus.

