1. INTRODUCTION

1.1 Background on Condition

Uterine leiomyomas (fibroids) represent a formidable clinical problem. With an incidence of 50-80% of women by age 50 (3), they are the most common tumors of the female reproductive tract (4). They are characterized by smooth muscle cellular proliferation and excessive disordered extracellular matrix. The medical and economic burden of fibroids is significant with estimated annual fibroid-related costs in the US of \$5.9-34.4 billion (5). Although hormonal treatments including oral contraceptives are used, efficacy remains limited. Treatment with Gonadotropin-releasing hormone (GnRH) agonists results in tumor shrinkage (6). However, the effect is usually transient and has significant side effects which prohibits long term use (7). Thus, uterine artery embolization and surgery are required in many cases. In fact, symptomatic fibroids are the most common indication for hysterectomy in the US (8). Myomectomy is a fertility-preserving alternative to hysterectomy but it is an invasive procedure including complications in subsequent pregnancies. Thus, there is an urgent need for a novel long term non-hormonal treatment for uterine leiomyomas.

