4. SELECTION AND ENROLLMENT OF STUDY SUBJECTS

4.1 Inclusion Criteria

To be eligible, subjects must meet all of these criteria:

- 4.1.1 Signed informed written consent
- 4.1.2 Gender: female
- 4.1.3 Age: 18-55 years at time of signing consent
- 4.1.4 BMI of subjects: $< 45 \text{ kg/m}^2$
- 4.1.5 Uterine fibroids:
 - 4.1.5.1 Diagnosed by ultrasound (MRI will be used only if ultrasound is inconclusive)
 - 4.1.5.2 Number: any number of fibroids
 - 4.1.5.3 Location: submucosal or intramural
 - 4.1.5.4 At least one fibroid of diameter $> 3\text{cm}$
- 4.1.6 Symptoms: one or more of the following symptoms of Heavy menstrual bleeding (HMB), defined as:

Experienced cyclic (22 to 35 days) abnormal uterine bleeding (heavy or prolonged) in at least 3 of the last 6 menstrual periods, including menstrual bleeding lasting 5 or more days or heavy bleeding per participant recall. Examples of heavy bleeding may include, but are not limited to the following:

 - 4.1.6.1 Requires the use of double protection to manage menstrual bleeding

- 4.1.6.2 Menstrual bleeding accompanied by the sensation of “gushing” or “flooding”
- 4.1.6.3 Saturates more than 1 tampon or sanitary pad per hour for 3 or more consecutive hours
- 4.1.6.4 Regularly needs to change the tampon or sanitary pad at night or regularly soils bedclothes
- 4.1.6.5 Heavy bleeding that affects work, school, or social activities
- 4.1.6.6 Pelvic pain/ pressure likely caused by fibroids
- 4.1.7 Plan for surgery (hysterectomy or myomectomy)
- 4.1.8 Normal Pap smear within the last year
- 4.1.9 Use of contraception during study such as non-hormonal contraceptives, intrauterine devices (IUD)/ intrauterine systems (IUS), barrier contraceptives, abstinence or sterilization

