4.2 Exclusion Criteria

To be eligible, subjects must not meet any of these criteria:

- 4.2.1 Pregnancy or lactation.
- 4.2.2 History or current uterine, cervical or ovarian cancer.
- 4.2.3 Current endometrial hyperplasia or history of atypical endometrial hyperplasia. Endometrial biopsy will be done during screening if not done within last 12 months.
- 4.2.4 Suspicion of leiomyosarcoma.
- 4.2.5 Recent rapid growth of fibroids (i.e. doubling in size within 1-6 months period).
- 4.2.6 Unevaluated gynecologic abnormalities (unexplained vaginal bleeding, cervical dysplasia, or abnormal adnexal/ovarian mass).
- 4.2.7 Menopausal status.
- 4.2.8 Surgery is urgently indicated (<3 months) for medical or social reasons.
- 4.2.9 Hemoglobin \leq 6 g/dL.
- 4.2.10 Currently enrolled in another investigational study.
- 4.2.11 Mental condition or other barrier preventing informed written consent. Allergy or hypersensitivity to simvastatin.
- 4.2.12 Current use of simvastatin or other drugs of the same class.
- 4.2.13 Concomitant administration of strong CYP3A4 inhibitors including itraconazole, ketoconazole, posaconazole, voriconazole, erythromycin, clarithromycin, elithromycin,

HIV protease inhibitors, boceprevir, telaprevir, nefazodone, and cobicistat-containing products.

- 4.2.14 Concomitant administration of gemfibrozil, cyclosporine, or danazol, verapamil, diltiazem, amiodarone, diltiazem, dronedarone, amlodipine, ranozoline, lopitamide, and grapefruit juice.
- 4.2.15 Active liver disease, which may include unexplained persistent elevations in hepatic transaminase levels.(elevation of AST and/or ALT > 2 s.d. above the normal range at screening visit)
- 4.2.16 Known increased risk or diagnosis of a myopathy.

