5.3 Concomitant Medications

No medication will be given outside of the study drug simvastatin or the placebo except for treatment of conditions that are clinically indicated. Prophylactic antibiotics may be given prior to hysterectomy or myomectomy based on standard pre-operative procedures at the research site.

Prescription or over-the-counter systemic medications will be allowed at the discretion of the investigators. Medicines will be allowed for depression, headache migraines, allergies, hypertension, and other medical conditions that are not part of the exclusion criteria.

All women will be protected from pregnancy by intrauterine devices (IUD)/ intrauterine systems (IUS), barrier contraceptives, abstinence or sterilization for the duration of the study.

All concomitant medication must be recorded in the subject's medical records. Additionally, any diagnostic, therapeutic, or surgical procedure performed during the study period will be recorded including the date, indication, and description of the procedure(s) and any clinical findings.

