6.2 Visit Description

6.2.1 Scheduled Visits

For the timing of each visit, see Table 1. Site personnel will determine the start of each treatment period and the participants will be informed about the visit dates.

Visit 1: Screening visit

The following procedures will be performed during this visit:

- Informative discussion about the study and obtaining of the informed consent.
- Obtain signed and dated informed consent.
- Subject identification number assigned.
- Assess inclusion/ exclusion criteria.
- Demographic data, smoking history, and alcohol consumption.
- Medical, reproductive, menstrual, and fibroids histories.
- Prior and concomitant medications the subject is taking.
- Information about adverse events assessment.
- Physical examination, gynecological examination.
- Vital signs.
- Urine pregnancy test.
- Pap smear (may be waived if a normal result has been documented in the subject's medical record within the previous 12 months).
- Endometrial biopsy if not done in the last 12 months.
- Ultrasound for fibroid location, size, and MRI only if the ultrasound is inconclusive.
- Laboratory evaluations: CBC with differential, hemoglobin, hematocrit, ferritin, liver enzymes and lipid panel. Urine pregnancy test.
- Instruct the subject to complete the questionnaires.

Visit 2: Drug intake initiation visit

If the subject is eligible for the study based on the screening visit information, the subject will be invited to come for the second visit.

The study subjects will be randomized into 12 weeks of simvastatin (40 mg/day orally) or placebo arms (1:1). We will use stratified block randomization with randomly permuted blocks of sizes 4 and 6 into one of the two arms.

The randomization scheme will be stratified by race/ethnicity in three categories: African American, Caucasian, and Hispanic. All other races will be excluded (small numbers precludes proper stratification and analysis). The stratification will ensure similar distribution of

race/ethnicity categories across the arms. This is a double-blinded study, neither subjects nor interacting personnel will know arm designation.

This is an “add-on” study, i.e. subjects in both arms will continue their current treatments excluding hormonal contraceptives and medications contraindicated as per prescribing information for simvastatin.

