6.3 Study Outcomes

The primary outcome will be to assess the preliminary clinical efficacy of simvastatin in reducing size of fibroids. The study will also evaluate the effects of simvastatin on fibroid related symptoms. This will be done by collection of data on symptoms and health related quality of life as obtained through questionnaires and by maintaining a daily log of symptoms on a subject diary during the treatment period of the study.

For the safety outcomes, the study will evaluate the percentage of adverse events (AE) and serious adverse events (SAE) by organ systems, including signs/symptoms, laboratory values, and clinical events.

We will also compare hemoglobin, hematocrit, ferritin, liver enzymes and lipid panel pre and post-study.

For the secondary objectives to characterize the molecular, cellular and histologic effects of simvastatin on human fibroids, the tissue will be characterized using TUNEL and immunoblotting techniques.

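### The add-on rule lets women continue GnRH agonists, which the protocol says shrink fibroids, although fibroid size is the primary outcome

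*Protocol*

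**What the plan says.** Section 3.3 describes an add-on trial in which "subjects in both arms will continue their current treatments for fibroids except hormonal birth control and medications contraindicated as per simvastatin prescribing information". The Visit 2 text in section 6.2.1 repeats this, again "excluding hormonal contraceptives and medications contraindicated as per prescribing information for simvastatin".

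Section 1.1 says of one fibroid treatment: "Treatment with Gonadotropin-releasing hormone (GnRH) agonists results in tumor shrinkage (6"). It adds that the effect is usually transient and that side effects rule out long-term use. Section 6.3 reads: "The primary outcome will be to assess the preliminary clinical efficacy of simvastatin in reducing size of fibroids".

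The drug exclusions in 4.2.13 and 4.2.14 are a simvastatin interaction list. Danazol appears there ("Concomitant administration of gemfibrozil, cyclosporine, or danazol, verapamil, diltiazem, amiodarone"), and GnRH agonists do not. Section 4.1.9 allows intrauterine systems without limiting them to non-hormonal devices.

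Section 5.3 opens by confining drugs other than study medication to clinically indicated treatment, then says "Prescription or over-the-counter systemic medications will be allowed at the discretion of the investigators".

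Two criteria act as indirect filters. Section 4.1.6 asks for "Experienced cyclic (22 to 35 days) abnormal uterine bleeding (heavy or prolonged) in at least 3 of the last 6 menstrual periods", and an exclusion reads "4.2.7 Menopausal status".

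**The concern.** The background section identifies a treatment that changes the primary outcome, and the treatment rules leave it open. A woman who began a GnRH agonist shortly before screening can still meet the bleeding criterion, because it looks back over six periods. She may then be in an active phase of shrinkage between the Visit 1 and week-12 scans, so part of her volume change reflects the other drug. Because section 1.1 says long-term use is ruled out, recent short-course users are the likelier ones, and the indirect filters are weakest for them.

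At stake is precision, and how clearly a size result can be attributed to simvastatin, in a trial with 30 women per arm. A start during treatment is a separate matter: it happens after randomisation and could differ by arm, but the protocol gives no basis for the number or direction of such starts.

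**Working it through.** **Reading check.** Each place where a GnRH agonist could be barred:

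| Place | Does it bar a GnRH agonist? |
|---|---|
| 3.3 and 6.2.1, exceptions to the add-on rule | No. It is not birth control, and no visible text lists it as contraindicated with simvastatin (the appended prescribing information is not in the text available). |
| 4.1 inclusion | Indirectly, through recent cyclic bleeding; a recent starter passes |
| 4.2 exclusion | Indirectly, through menopausal status; no drug exclusion, no washout |
| 5.3 concomitant drugs | Restricts starts to clinical need and investigator judgement; no bar |

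**Size.** The plan has no figure to reproduce here. Taken from the protocol: 30 per arm (3.2) and the 20% effect (3.2), read here either as 20 points of volume change or as a 20% lower volume. Everything else is assumed: the fraction of users *p*, the extra shrinkage *g* in a user, the SD *s* without users, and two-sided alpha 0.05. Users are spread at random over both arms, so

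SD with users = √(s² + p(1−p)g²),

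and power comes from the two-sample t-test with 58 degrees of freedom and noncentrality difference / (SD·√(2/30)). The mixture is treated as roughly normal.

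*Basis A: percent volume change (section 2.1 compares volume before and after).* s = 25, g = 40, difference 20:

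| Users | Variance | SD | Power | Equivalent n per arm (30 × 625 / variance) |
|---|---|---|---|---|
| 0% | 625 | 25.00 | 86.1% | 30 |
| 2% | 625 + 0.0196 × 1600 = 656.4 | 25.62 | 84.4% | 28.6 |
| 5% | 625 + 0.0475 × 1600 = 701 | 26.48 | 82.0% | 26.7 |
| 10% | 625 + 0.09 × 1600 = 769 | 27.73 | 78.4% | 24.4 |

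Varying s over 20, 25, 30 and g over 30, 40, 50, the loss in power points is 0.6-2.6 at 2% users, 1.6-6.4 at 5%, and 3.3-11.8 at 10%. The largest loss is at s = 25, g = 50 (86.1% to 74.3%).

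*Basis B: week-12 size itself (section 9 centres the primary analysis on 12-week outcomes).* On the log scale, a 20% reduction is −ln(0.8) = 0.223 and a 40% shrinkage in a user is −ln(0.6) = 0.511. With s = 1.0 and 10% users, the variance is 1 + 0.09 × 0.511² = 1.0235. Power goes from 13.6% to 13.4%, a loss of 0.2 points. Over s = 0.6-1.2 and shrinkage 30-50%, the loss runs from under 0.1 point (10.92% to 10.87%) to 2.6 points (29.4% to 26.8%).

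Chance imbalance in users between arms is what the p(1−p)g² term represents, so it is not added again. For scale, on basis A a gap of two users moves the arm difference by 2 × 40/30 = 2.7 points, against a standard error of 25 × √(2/30) = 6.5, or about 0.4 standard errors.

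**The case against.** The case for leaving the text alone has several parts.

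- **The add-on design is deliberate.** It is stated twice, and closing it to other fibroid drugs is partly a matter of preference. This stands as a reason to grade the point low. It does not explain why hormonal birth control is stopped, when section 1.1 calls the efficacy of hormonal treatment limited, while the drug class it credits with shrinkage may continue.
- **Few or no women may be affected.** The bleeding and menopausal criteria should remove many established users, and nothing in the protocol suggests how many others would enrol. This stands, and it is why no prevalence is claimed.
- **Section 5.3 already limits new starts.** A start needs a clinical indication, falls under investigator judgement, and would be recorded. This stands in part: it is tighter than open permission, but women with symptomatic fibroids awaiting surgery could meet it.
- **Section 9 can adjust.** Medications are recorded from Visit 1, and an unbalanced, predictive history variable could enter the final model. That could recover some precision for use at entry. It does not reach drugs started after randomisation.
- **On week-12 size the loss is close to nil.** This is correct under the stated SDs; the larger figures depend on analysing percent change.

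A reader might infer that the protocol set out to remove all fibroid-active drugs and failed. The text does not support this: danazol is listed only for its interaction with simvastatin, and intrauterine systems are allowed without a non-hormonal limit.

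**Conclusion.** The gap is real and its cost is probably modest. Women may continue a GnRH agonist under sections 3.3 and 6.2, and section 5.3 restricts but does not prevent starting one before the week-12 scan. This assumes that the appended prescribing information, which is not visible, does not list the class as contraindicated.

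A reader might infer that the treatment comparison is biased. For use at entry the design does not support that: randomisation and blinding leave no expected bias, only added variance. For starts during treatment, bias is possible in principle, but nothing in the document indicates its direction or size, and no figure is claimed.

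The cost is about 1 to 12 power points on percent volume change (SD 20-30, shrinkage 30-50 points, 2-10% users), and about 0.2 points on week-12 log volume at SD 1.0 with 10% users. If there are hardly any users, it is negligible. The point is an inexpensive improvement, not a flaw that threatens the trial.

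**What to change.** 1. In 4.2, exclude current or recent use of GnRH analogues and other drugs given to shrink fibroids, over an interval before the Visit 1 scan that the investigators set.
2. Add the same drugs to the exceptions in 3.3 and 6.2.
3. In 5.3, state that these drugs are not to be started before the week-12 ultrasound unless medically necessary. A woman who does start one stays in her randomised arm, is scanned at week 12, and is reported by arm.

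This changes wording in four sections. It adds no procedure and leaves scan timing as it is. The downside is that a few otherwise eligible women are lost or delayed, in a trial that already allows for 5 years to accrue 60 evaluable women (10.2). If users are rare, that loss is correspondingly small.

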3.3.1 Study Group

The 30 participants randomized in this group will intake 40mg / day of simvastatin orally at the same time in the evening, every day for the study duration of 12 weeks prior to undergoing hysterectomy/ myomectomy. The fibroid sample will be collected after the surgery to evaluate the effects of the study medication on the fibroid tissue.

3.3.2 Placebo Group

The 30 participants randomized in this group will intake 40mg / day of placebo orally at the same time in the evening every day for the study duration of 12 weeks prior to undergoing hysterectomy/ myomectomy. The fibroid sample will be collected after the surgery to evaluate the effects of the study medication on the fibroid tissue.

3.4 Study Duration

The participants will be enrolled in the study for a duration of 18-20 weeks. They will be visiting the study site 4 times for the study related visits and will be seen by the study team for follow up after their hysterectomy or myomectomy during their scheduled post-operative visits with their gynecologist. The first visit is the screening visit to obtain the informed consent and assess if the subject is eligible to participate in the study.

The study visits include:

1. Visit 1: Screening visit
2. Visit 2: Drug intake initiation visit at 0 weeks
3. Visit 3: 6 weeks after visit 2 during treatment period

4. Visit 4: 6 weeks after visit 3 during the treatment period

Follow up visits: Scheduled at subject's post-operative visits with their gynecologist for follow up.

The participant will receive the study medication at the treatment visits (Visit 2 and 3) for the next 6 weeks and study related assessments will be done at each of these visits. The study nurse will also remain in contact with the participant for the 12 week duration weekly to enhance compliance to study medication intake and to record adverse events if any.

The study nurse will also perform a drug reconciliation at each of the study visits to ensure that the patient is adherent to the study drug medication. The subjects will be instructed to bring all the medications that they forgot to intake or were left at the time of the research visit, these will be counted by the study nurse and a log of this information will be kept by the study research team. The regular weekly reminder calls from the study team will also complement the delivery of information about restricted food items such as grape fruit, cranberry juice for the intervals when the subject is not visiting the research team at Johns Hopkins Outpatient Clinic.

The subject undergoes hysterectomy or myomectomy at the end of treatment period (Visit 4) at week 12 and samples are obtained to study the fibroid tissue for molecular, cellular and histologic effects of simvastatin on human leiomyoma tissues. The study team will collect a 2.5 X 2.0 X 1.0 cm (or up to half of the tumor size) tissue sample from one fibroid for this study after the surgical pathology team has completed a preliminary evaluation of the delivered uterus. This tissue sample will undergo histopathological evaluation to study the effects of the study drug on fibroids.

We do not anticipate having a participant in this study who will have an unexpected diagnosis of leiomyosarcoma. We will keep all tissue sections and samples until the final pathology report is made and are capable of returning tissue to the pathologist for evaluation, if necessary. Even when the patient has had a hysterectomy or myomectomy, the collected fibroid itself is not manipulated at the time of surgery, minimizing any untoward cell spillage into the peritoneal cavity. In the highly unlikely event that we do enroll a subject with the final pathological diagnosis of leiomyosarcoma we will treat this as a serious adverse event and report it immediately.

A double blinded, phase II, randomized controlled trial to study the effects of simvastatin in patients with uterine leiomyoma.

The subjects will be scheduled to undergo surgery within 1 week following the 12 weeks treatment period of the study.

Standard clinical care will be provided pre and post hysterectomy/ myomectomy to the participants independent of the study assessments. The study nurse will follow up with the study participants during their 2 and 6 weeks post-operative visits with the subject's gynecologist.

More detailed information about the study visits and study related procedures is shown in Figure 1 and Table 1 below.

Study Design: Flowchart of the study design can be seen in Figure 1 below.

A double blinded, phase II, randomized controlled trial to study the effects of simvastatin in patients with uterine leiomyoma.

[figure not shown]

Figure 1: Study design flowchart.

Table 1: Detailed Flowchart of Study Assessments

A double blinded, phase II, randomized controlled trial to study the effects of simvastatin in patients with uterine leiomyoma.

Visit	Visit 1	Visit 2	Visit 3	Visit 4	Follow up Visit
Activity	Screening	Beginning of the treatment period	6 weeks after start of treatment period	12 weeks after start of treatment period	Scheduled at 2 and 6 weeks post surgery
Informed Consent	X				
I/E criteria	X				
Demographics	X				
Smoking/Alcohol History	X				
Medical History	X				
Reproductive, menstrual, fibroid history	X				
Medication reconciliation & restricted food discussion	X	X	X	X	
Vital signs	X	X	X	X	
Physical examination	X			X	
Gynecological exam	X			X	
Cervical smear	X				
Ultrasound examination	X			X	
Endometrial biopsy	X				
Labs	X			X	
Inform about contraception	X	X	X	X	

A double blinded, phase II, randomized controlled trial to study the effects of simvastatin in patients with uterine leiomyoma.

Dispense/ collect / review subject diary for fibroid related symptoms	X	X	X	X	X
Home urine pregnancy test	X	X	X	X	
Randomization	X				
Drug accountability		X	X	X	
Drug dispensation		X	X		
Adverse event monitoring		X	X	X	X
Assess subject compliance		X	X	X	
Questionnaires	X	X	X	X	X

